19.0 Risks to Subjects

19.1 List the reasonably foreseeable risks, discomforts, hazards, or inconveniences to the subjects related to their participation in the research. Consider physical, psychological, social, legal, and economic risks. Include a description of the probability, magnitude, duration, and reversibility of the risks.

NOTE: Breach of confidentiality is always a risk for identifiable subject data.

Response:

While being asked about depression in the past week, participants may be upset. We consider this as a minimal risk. But if the data shows that the participant is depressive, we will take an immediate action described above.

While a caregiver is helping the care recipient's activities of daily living using a new technique that are learned from us, such as a new transfer method, they may make a mistake and fall and have an injury. However, prevention of falls is one our study purpose.

19.2 Describe procedures performed to lessen the probability or magnitude of risks, including procedures being performed to monitor subjects for safety.

Response:

If a participant appears to be upset, the interviewer (OTGS) will ask if he/she would like to continue the interview or not. If they wants to continue after

a little rest, the interview will be resumed. If not, an interview at another time will be asked to complete the interview and make an appointment. In addition, if he/she scores 15 or more in the total CES-D, it will be informed to the participant and the PACE. The PACE may inform the PI about withdrawal of the participant from this study. We do not know the PACE criteria for the decision, but we will follow the PACE's decision.

Physical injury may occur while assisting care recipients' activities of daily living, but the purpose of the study is to prevent that. Any newly learned methods may cause discomfort or a fall, if the method is applied in a wrong way. Therefore, OTGS will show an intervention and caregivers will practice it until they become comfortable. An illustrated instruction will be provided for caregivers, if necessary or requested.

19.3 If applicable, indicate which procedures may have risks to the subjects that are currently unforeseeable.

Response:

Assisting transfer from a bed to a standing position and getting up from a couch.

If applicable, indicate which research procedures may have risks to an embryo or fetus should the subject be or become pregnant.

Response: N/A

19.4 If applicable, describe risks to others who are not subjects.

Response:

It is possible that caregivers' response to the study may upset their care recipients. Therefore, the structured interview will take place that the care recipient is not present.

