A month after initial assessment, OTGS will contact CRs for follow-up and 2 months later, the posttest will be administered. At 4 months, follow-up interview will occur. The number of home visits (4-6) will vary depending on case. Finally 6 months after the intervention, a phone call will be made, asking the same questions before and the number of falls and emergency visits of care recipients in the past 10 months. After each interview, a participant will be paid \$20. (The total maximum is \$80).

9.2 Describe what data will be collected.

NOTE: For studies with multiple data collection points or long-term follow up, consider the addition of a schedule or table in your response.

Response:

The outcome measures will use established instruments. To measure caregiver burden, 12-item Zarit Burden Interview (ZBI), for depression, 20-item Center for Epidemiology Study-Depression (CES-D) will be used. Positive Aspect of Caregiving has 9 items. Self-esteem and fatigue questions will use a visual analog scale from 1 to 10. In addition, items of activities of daily living (ADL, e.g., eating, dressing, and toileting) and instrumental ADL (IADL, e.g., meal preparation, housekeeping) that caregivers are assisting will be identified. We do not assess or provide interventions for CRs directly, but we ask caregivers about CR's cognitive levels using Global Deterioration Scale, and functional levels using FIM to assess ADL and OARS' IADL. We also ask if care recipients fell or visited an emergency room.

 *9.3 List any instruments or measurement tools used to collect data (e.g. questionnaire, interview guide, validated instrument, data collection form).*

Include copies of these documents with your submission.

Response:

The assessment form is attached.

9.4 Describe any source records that will be used to collect data about subjects (e.g. school records, electronic medical records).

Response:

We will not use other sources or records. But if the cause of cognitive impairment is not clear, we will ask the PACE to provide it for us. This is written in the consent form.

*9.5 Indicate whether or not **individual** subject results, such as results of investigational diagnostic tests, genetic tests, or incidental findings will be shared with subjects or others (e.g., the subject's primary care physician) and if so, describe how these will be shared.*

Response:

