17.0 Provisions to Monitor the Data to Ensure the Safety of Subjects

- N/A: This study is not enrolling subjects, or is limited to records review procedures only. This section does not apply.

NOTE: *Minimal risk studies may be required to monitor subject safety if the research procedures include procedures that present unique risks to subjects that require monitoring. Some examples include: exercising to exertion, or instruments that elicit suicidality or substance abuse behavior. In such cases, N/A is not an acceptable response.*

17.1 Describe the plan to periodically evaluate the data collected regarding both harms and benefits to determine whether subjects remain safe.

Response:

We will not periodically evaluate the data collected but we will collect data every 2 months for three times. The study will identify depression. If the total score of CES-D is 15 or higher at the time of interview, this will be reported to the participant and the PACE for an appropriate intervention.

17.2 Describe what data are reviewed, including safety data, untoward events, and efficacy data.

Response:

The total score of the Center for Epidemiology Study-Depression will be used to detect depression, which is a considered mental illness.

17.3 Describe any safety endpoints.

Response:

The CES-D total score of 14 or less (not depressive) and 15 or higher (indicative of depressive symptom). One of the purpose of the study is to decrease the CES-D score.

17.4 Describe how the safety information will be collected (e.g., with case report forms, at study visits, by telephone calls with participants).

Response:

Face-to face interviews.

17.5 Describe the frequency of safety data collection.

Response:

Three times in 4 months.

17.6 Describe who will review the safety data.

Response:

Study OTGS and the PI

17.7 Describe the frequency or periodicity of review of cumulative safety data.

Response:

We do not have cumulative safety data. When each time we interview participants, we will review the data.

17.8 Describe the statistical tests for analyzing the safety data to determine whether harm is occurring.

Response:

The sum of 20 item CES-D scores will be used.

17.9 Describe any conditions that trigger an immediate suspension of the research.

Response:

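### Caregiver falls and injuries from newly taught techniques are a named risk, but the protocol text describes no systematic recording or tabulation of them in either arm

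*Combined protocol and SAP*

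**What the plan says.** Section numbers are those in the body of the protocol; the table of contents numbers them differently.

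**The risk.** Section 19.1 describes a caregiver applying a technique learned from the study team: "such as a new transfer method, they may make a mistake and fall and have an injury". Section 19.2 returns to it: "Any newly learned methods may cause discomfort or a fall, if the method is applied in a wrong way". It also says "Physical injury may occur while assisting care recipients' activities of daily living, but the purpose of the study is to prevent that". Section 19.3 again points to assisted transfers.

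**The response to the risk.** Section 19.2 relies on training: "Therefore, OTGS will show an intervention and caregivers will practice it until they become comfortable". An illustrated instruction is offered where needed or requested.

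**The safety data.**
- 17.2, data reviewed: "The total score of the Center for Epidemiology Study-Depression will be used to detect depression".
- 17.3, safety endpoint: "The CES-D total score of 14 or less (not depressive) and 15 or higher (indicative of depressive symptom").
- 17.8, statistic for harm: "The sum of 20 item CES-D scores will be used".
- 17.4 and 17.5 place safety collection in face-to-face interviews, three times over 4 months. 17.7 says there are no cumulative safety data.

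**The falls data.** The final call in 9.1 is described as "asking the same questions before and the number of falls and emergency visits of care recipients in the past 10 months". Section 9.2 likewise asks about falls and emergency-room visits of care recipients. Section 16.1 compares falls and emergency visits between groups with a Mann-Whitney test.

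**The concern.** The protocol handles its two named risks to caregivers very differently. Distress or depression has an instrument, a threshold and an immediate reporting route (9.6, 17.1 to 17.3). Physical injury has a preventive step but no described question, record or table. Practising a transfer until comfortable may lower the chance of injury; it does not show whether injuries occurred.

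The trial could therefore report lower burden without any planned data on whether the taught techniques hurt the people using them. The investigator would also have no routine means of noticing, during the trial, that a particular technique was associated with injuries. The efficacy analyses are unaffected. What is at stake is what the trial can say about safety.

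**Working it through.** **1. Is caregiver injury captured anywhere in the text?** Each place where it could be:

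| Section | What is collected or planned | Caregiver fall or injury? |
|---|---|---|
| 1.2 | Falls and emergency visits of care recipients | No |
| 9.1, interview | Burden, fatigue, depression, positive aspects, self-efficacy | No |
| 9.1, final call | Same questions, plus care-recipient falls and emergency visits | No |
| 9.2 | Named scales, help given, care-recipient function, falls and emergency visits | No |
| 9.3 | Assessment form, attached but not among the documents | Cannot be checked |
| 16.1 | Mann-Whitney on falls and emergency visits, which 1.2 and 9.1 define for care recipients | No |
| 17.2, 17.3, 17.8 | CES-D total | No |
| 21.2 | Consent wording that caregiver injury is not compensated | Mentioned, not measured |
| 23.4 | Phone contacts on whether solutions work and the next appointment | No question or record specified |

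No section of the text describes an injury item, an adverse-event form or a count of caregiver falls.

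**2. Group size.** Sections 4.3 and 16.2 give d = 0.65, directional α = 0.05, 80% power and 30 per group. Check: n = 2(1.645 + 0.842)² / 0.65² = 12.37 / 0.4225 = 29.3, rounded up to 30. The t-based solution is 29.97. The figure reproduces, so 30 is used below.

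**3. What a count could show.** The documents give no injury rate; 2%, 5% and 10% over follow-up are assumptions. Interventions are individualised (9.1), and some examples, such as education, incentives, calendars and day care, involve no physical technique. The number exposed may therefore be well below 30; 10 is used as an assumed lower case.

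- Chance of at least one event: 1 − (1 − p)^n.
- One-sided 95% upper limit after zero events: 1 − 0.05^(1/n).

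| Exposed n | p = 2% | p = 5% | p = 10% | Upper limit, 0 events |
|---|---|---|---|---|
| 30 | 1 − 0.98^30 = 45% | 1 − 0.95^30 = 79% | 1 − 0.90^30 = 96% | 1 − 0.05^(1/30) = 9.5% |
| 10 | 1 − 0.98^10 = 18% | 1 − 0.95^10 = 40% | 1 − 0.90^10 = 65% | 1 − 0.05^(1/10) = 26% |

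**4. Could the arms be tested against each other?** Not usefully. For assumed rates of 5% and 15% with 30 per arm and two-sided α = 0.05, power is about 25%. The counts would be descriptive.

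**The case against.** A reader might infer that physical harm from the intervention is never counted at all. The documents do not support that. Care-recipient falls and emergency visits are collected and compared between groups, and a failed transfer can bring down the care recipient as well as the caregiver. Part of the physical harm is therefore captured, though as an outcome and on recall of up to 10 months. The gap concerns caregivers.

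A reader might also infer that a caregiver injury could not be detected or acted on. That goes too far as well. Section 9.1 plans a contact at one month and 4 to 6 home visits, 23.4 adds phone contacts about whether solutions work, and 16.1 rates how effective the solutions were. An injury could well be mentioned in any of these. Nothing in the text says it would be asked about, written down or tabulated.

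The sentence in 19.2 that makes injury prevention a purpose of the study should not be pressed. Caregiver injury is not among the hypotheses or endpoints, and 9.1 justifies its fall-prevention work by the fall rate of PACE enrollees. No stated study question goes unanswered.

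Two further objections stand. The assessment form is unseen and might contain an injury item. And the 9.5% limit holds only if all 30 treated caregivers are taught a physical technique. Neither removes the mismatch between Sections 19 and 17: if the form does carry such an item, 17.2, 17.3 and the analysis section still need to name it.

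**Conclusion.** The point holds for caregivers and for systematic recording. The protocol foresees falls and injuries to its own subjects from the techniques it teaches, makes the CES-D its only stated safety measure, and describes fall and emergency-visit questions about care recipients only. On the protocol text, the trial would end with no planned count of caregiver falls or injuries in either arm. This rests on the text alone, because the attached form could not be checked.

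The gain from closing the gap is real but modest. A count would probably reveal a common problem: at a true 10% rate, the chance of at least one event is 96% with 30 exposed and 65% with 10. Zero events would exclude only rates above 9.5% or about 26% respectively. The event rates and the figure of 10 exposed are assumptions. No efficacy conclusion depends on this, but the change is cheap and should be made.

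**What to change.** - Add one item to the assessment form at the 2-month, 4-month and final assessments, in both arms: whether the caregiver has fallen or been hurt while helping the care recipient since the last interview. If so, record the date, the activity, whether a taught method was in use, and whether medical care was needed.
- List caregiver falls and injuries in 17.2 and 17.3. Update 17.4 and 17.5, which cover only face-to-face interviews in the first 4 months, to include the final phone assessment.
- Have the interviewer notify the investigator of any positive answer. Keep this a recording step, with no withdrawal or other clinical rule attached. Reusing the CES-D pathway unchanged would not do that: it continues to PACE (9.6), which may then inform the investigator of a participant's withdrawal (19.2).
- In 16.1, plan counts by arm, reported descriptively. For the treated arm, also give the number of caregivers who were taught a physical technique as a second denominator.

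**Cost.** About a minute at each of three interviews that already take place, one form revision and an IRB amendment; no extra visits or staff. Treated caregivers may recall technique-related events more readily than controls. On the timeline in 16.1 the last interval runs from 4 to 10 months, so recall there spans about six months. Both are reasons to keep the counts descriptive.

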We will share the solutions with caregivers but not the score of outcome measures, unless the score of CES-D is 15 or higher (indicative of depressive symptoms). This will be shared with PACE because their program include not only care recipients but also their caregivers.

*9.6 Indicate whether or not **study** results will be shared with subjects or others, and if so, describe how these will be shared.*

Response:

At the assessment, if a caregiver scores 15 or higher for the CES-D, the interviewer will inform him/her about the result and contact the PI immediately. The PI will report it to the PACE immediately. The PACE will respond to this situation according to their policy. The policy for caregivers is instituted because they are integral part of the care recipient's ability to continue living in the community. Other assessed results will not be shared with participants, but aggregated data will be shared with the PACE. This include problems and solutions.

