If the CES-D score is 15 or higher, it will be reported to the PACE for possible intervention, in accordance with their policy. We do not have any conditions that will be used for immediate suspension of the participant form our research.

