18.0 Withdrawal of Subjects

 N/A: This study is not enrolling subjects. This section does not apply.

18.1 Describe anticipated circumstances under which subjects may be withdrawn from the research without their consent.

Response:

We will not withdraw a participant from the research without their consent.

18.2 Describe any procedures for orderly termination.

NOTE: Examples may include return of study drug, exit interview with clinician. Include whether additional follow up is recommended for safety reasons for physical or emotional health.

Response:

If a participant decide to withdraw for the study, he/she will indicate it to an OTGS at the interview and the PI will confirm the wish through a phone contact with the participant.

18.3 Describe procedures that will be followed when subjects withdraw from the research, including retention of already collected data, and partial withdrawal from procedures with continued data collection, as applicable.

Response:

After the orderly termination, the data that had been collected until the withdrawal will be retained and analyzed. This information is included in the informed consent.

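### Section 18.1 rules out withdrawal without consent, but 19.2 follows a PACE withdrawal decision after a CES-D of 15 or more, and no later interviews are provided for

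*Combined protocol and SAP*

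**What the plan says.** Section 18.1 asks when a subject may be withdrawn without consent. The answer is "We will not withdraw a participant from the research without their consent".

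Section 19.2, on lessening risk, says that a CES-D total of 15 or more is made known to the caregiver and to the PACE. It goes on: "The PACE may inform the PI about withdrawal of the participant from this study". It adds "We do not know the PACE criteria for the decision, but we will follow" what the PACE decides.

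The prompt in 18.3 asks about "partial withdrawal from procedures with continued data collection, as applicable". The response says only that "the data that had been collected until the withdrawal will be retained and analyzed".

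Other sections deal with the same score without mentioning withdrawal. Section 9.6 says "The PACE will respond to this situation according to their policy", and 17.9 says "it will be reported to the PACE for possible intervention, in accordance with their policy". Depression is half of the primary endpoint (Scientific Endpoints, 2.1), and 9.2 names the CES-D as its measure.

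**The concern.** Staff with a flagged caregiver who wants to stay have two opposite instructions. Under 18.1 the caregiver stays; under 19.2 the caregiver leaves if the PACE says so.

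The statistical cost follows from the trigger. If the intervention lowers CES-D, more controls than treated caregivers will score 15 or more after baseline, so withdrawals that follow the score would fall more heavily on controls. Every later measure goes with the caregiver, including burden, the other primary outcome. The 10-month call is the most exposed visit, and the last research question in 1.2 (whether the effect persists) depends on it. The analysis plan in 16.1 describes no handling of missing data. The loss is avoidable, because the caregiver may still be willing to answer and the interviews are already scheduled.

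**Working it through.** **1. Do the sections reconcile?** Section 19.2 speaks of PACE criteria and a PACE decision, so it is not the caregiver's own wish passed on by the PACE. Section 18.2 covers only a participant who chooses to leave. Sections 9.6, 17.1 and 17.9 describe a PACE response, not removal. Nothing in the available text makes the PACE decision conditional on the caregiver's consent or on a stated safety reason.

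**2. The plan's own figure.** Sections 4.3 and 16.2 use d = 0.65, one-sided alpha .05 and 80% power. An exact one-sided t-test needs 29.97 per arm and has power 0.800 at 30 per arm, so the stated 30 per group reproduces. Recruiting 75 gives 37.5 per arm. With nobody lost, power is 87.4%.

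**3. Illustration of the loss.** The documents give no CES-D distribution and no PACE withdrawal rate, so these are assumptions: gamma scores limited to 0–60, control mean 15, SD 10, correlation 0.6 between visits, and an effect of 6.5 points (0.65 × 10) from month 2 on. Under them, 41% of controls and 21% of treated score 15 or more at month 2, and about the same at month 4. At either visit it is 56% and 32%; at both, 27% and 11%.

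Let p be the share of flagged caregivers whom the PACE withdraws.
- Retained at 4 months: 1 − p × (flagged at month 2).
- Retained at 10 months, one PACE decision per flagged caregiver: 1 − p × (flagged at either visit).
- Retained at 10 months, a fresh decision at each flagged visit: 1 − p × (flagged at month 2 + flagged at month 4) + p² × (flagged at both).

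At p = 0.25, before rounding the shares:
- 4 months: control 1 − 0.25 × 0.413 = 0.897; treated 1 − 0.25 × 0.215 = 0.946.
- One decision: control 1 − 0.25 × 0.557 = 0.861; treated 1 − 0.25 × 0.320 = 0.920.
- Two decisions: control 1 − 0.25 × 0.825 + 0.0625 × 0.269 = 0.81; treated 1 − 0.25 × 0.429 + 0.0625 × 0.109 = 0.90.

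Power uses the noncentral t with noncentrality 0.65 × √(n1·n2/(n1+n2)) and the 10-month numbers. For two decisions at p = 0.25, n is 30.4 and 33.8, the noncentrality is 0.65 × √16.0 = 2.60, and power is 82.3%.

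| p | 4 months, control / treated | 10 months, two decisions | Power | 10 months, one decision | Power |
|---|---|---|---|---|---|
| 0.10 | 96% / 98% | 92% / 96% | 85.4% | 94% / 97% | 86.0% |
| 0.25 | 90% / 95% | 81% / 90% | 82.3% | 86% / 92% | 83.7% |
| 0.50 | 79% / 89% | 66% / 81% | 76.5% | 72% / 84% | 79.0% |

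With two decisions at p = 0.25, power runs from 84% to 80% as the control mean goes from 12 to 18.

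**4. Other attrition.** The table treats PACE withdrawals as the only loss. With the planned 25% attrition, 75 × 0.75 = 56.25 remain, and power is Φ(0.65 × √(28.125/2) − 1.645) = Φ(0.79) = 0.79. If PACE withdrawals took a further 5%, 10% or 20% of those recruited, it would be 0.76, 0.73 or 0.67. The documents do not say whether the 25% already includes them.

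**5. Bias, same model.** With an effect that grows linearly to month 4, the GEE slope difference shrinks by 0.5–1.4% at p = 0.25 and 1.2–3.5% at p = 0.50. The lower figure is for an exchangeable and the higher for an independence working correlation. If every flagged caregiver were withdrawn, shrinkage would be 2.8–12.6%. With a step effect, the completers' repeated measures ANOVA contrast (months 2 and 4 minus baseline) shrinks by 0.9%, 2.4% and 9% at p = 0.25, 0.50 and 1. The 4-to-10-month comparison is off by about 0.1 and 0.2 points at p = 0.25 and 0.50 if the effect persists.

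**The case against.** The strongest reply is that little is at stake. Section 19.2 says only that the PACE may act. At 10% or 25% withdrawal, taken alone, power stays above the planned 80% and bias is about 1% or less. This stands: the case rests on the conflict in the text and an inexpensive repair, not on expected bias.

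The losses could also be smaller than tabulated. Many caregivers flagged at month 2 would already have been reported at baseline. If the PACE acted only on a first report, retention after baseline would be 94% vs 98% at p = 0.25 (power 86%) and 89% vs 96% at p = 0.50 (85%). Withdrawals at baseline are left out, because the documents do not say whether randomisation comes before the PACE could act on a baseline score.

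A PACE withdrawal after a depression alert may well come with a safety reason, so a safety exception could absorb part of the new rule. That is acceptable; what remains is the loss that no safety reason justifies. The consent form, not available here, may disclose the PACE route. That would narrow the conflict over consent but would not recover the missed interviews.

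A reader might take 17.9, "We do not have any conditions that will be used for immediate suspension of the participant", as a second contradiction of 19.2. It is weak support: the prompt there concerns immediate suspension of the research, not later withdrawal of one person by a third party.

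**Conclusion.** The concern holds. Sections 18.1 and 19.2 conflict, and 18.3 leaves no provision for follow-up of a caregiver who is withdrawn but still willing. Any PACE-directed withdrawal would cause avoidable loss that depends on a primary-outcome score and may differ by arm.

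A reader might infer that every caregiver scoring 15 or more is removed, or that the trial's comparison will be seriously biased. The documents do not support either. Withdrawal is only a possibility, its frequency is not stated, and in the illustration bias and power loss stay small unless the PACE withdraws about half or more of those flagged. All retention, power and bias figures rest on the assumed CES-D distribution, effect and withdrawal rate; the conflict between the sections does not. The change is worth making, but the results would not be invalid without it. Confidence is medium.

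**What to change.** Keep the CES-D report to the PACE as it is. Amend 19.2 and 18.3 so that a caregiver in either arm who still consents continues the scheduled 2-, 4- and 10-month outcome interviews and is analysed in the randomised group. The exceptions are a caregiver who declines and a specific safety reason from the PACE against interviewing. Record each PACE-directed withdrawal by arm, with the reason.

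If the PACE does not agree, correct 18.1 to disclose the PACE-directed route, and report those losses by arm.

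Two additions should be avoided. Caregivers should not be invited to skip the CES-D: 15.1 already lets them refuse any question, and an invitation would create missing scores among those likely to score high. Nor should the PACE be given a new power to stop intervention contacts, which the protocol does not describe and which could dilute treatment.

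The cost is protocol and consent wording, plus PACE agreement, which is not assured because the change narrows a decision that 19.2 now leaves to the PACE. No extra staff are needed: the interviews are already scheduled, and the last is a phone call.
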